7.1.2.2.2 Directed Physical Exam

Other than the Screening and treatment discontinuation visit, the investigator or qualified designee will perform a directed physical exam as clinically indicated prior to dosing on Day 1 of each treatment cycle (see Trial Flow Chart). New clinically significant abnormal findings should be recorded as AEs.

7.1.2.3 Vital Signs

The investigator or qualified designee will assess vital signs (including temperature, pulse, respiratory rate, and blood pressure) and weight at screening, prior to dosing on Day 1 of

each treatment cycle, and at treatment discontinuation as specified in the Trial Flow Chart. Height will be measured at screening only.

7.1.2.4 12-Lead Electrocardiogram

A standard 12-lead ECG will be performed using local standard procedures once at screening. Clinically significant abnormal findings should be recorded as medical history. Additional time points may be performed as clinically necessary.

7.1.2.5 Eastern Cooperative oncology Group Performance Status

The investigator or qualified designee will assess ECOG status (see Appendix 12.4) at screening, prior to dosing on Day 1 of each treatment cycle, at treatment discontinuation, and at progressive disease (PD) follow-up visit as specified in the Trial Flow Chart.

7.1.2.6 Tumor Imaging and Assessment of Disease

The process for image collection and transmission to the central imaging vendor can be found in the Site Imaging Manual. For this study, imaging of chest abdomen, and pelvis are required at Screening and at each scheduled disease assessment visit after enrollment. Computed tomography (CT) is the modality strongly preferred for chest. For abdomen and pelvis CT or magnetic resonance imaging (MRI) are both acceptable. However, the same imaging modality and technique, such as use of contrast should be used consistently for an anatomic region in a subject throughout the trial.

All scheduled images for all study subjects from the sites will be submitted to the central imaging vendor. In addition, additional imaging (including other modalities) that are obtained at an unscheduled time point to determine if the subject has progressed, as well as imaging obtained for other reasons but captures radiologic progression, should be submitted to the central vendor as well.

7.1.2.6.1 Screening Tumor Imaging

At Screening, imaging scans must be performed within 28 days prior to date of allocation. The site study team must review screening images to confirm the subject has measurable disease per RECIST 1.1. The screening images must be submitted to the central imaging vendor for confirmation of measurable disease per RECIST 1.1 for eligibility prior to allocation.

Scans performed as part of routine clinical management are acceptable for use as the screening scan if they are of diagnostic quality and are performed within 28 days prior to the date of allocation and can be assessed by the central imaging vendor.

Subjects with previously treated brain metastases may participate provided they have stable brain metastases, ie. without evidence of progression by imaging (confirmed by MRI if MRI was used at prior imaging, or confirmed by CT imaging if CT used at prior imaging for at least 4 weeks prior to the first dose of trial treatment; also, any neurologic symptoms must have returned to baseline), have no evidence of new or enlarging brain metastases, and have not used steroids for brain metastases for at least 28 days prior to trial initiation as per local

site assessment. This exception does not include carcinomatous meningitis, as subjects with carcinomatous meningitis are excluded regardless of clinical stability.

7.1.2.6.2 Disease Assessments During Treatment Period

After study start, study scheduled imaging assessments will be performed at 9 weeks (63 days \pm 7 days) from the date of allocation up to 54 weeks. Subsequent imaging should be performed Q12W (84 days \pm 7 days) or more frequently, if clinically indicated. Imaging timing should follow calendar days and should not be adjusted for delays in cycle starts or any dose interruptions that may occur. Imaging assessments should continue until disease progression per RECIST 1.1 or to confirm disease progression per irRECIST to avoid pseudoprogression (see Section 7.1.2.6.7 for details), the start of new anti-cancer treatment, withdrawal of consent, death, or notification by the Sponsor, whichever occurs first. All supplemental imaging must be submitted to the central imaging vendor.

Per RECIST 1.1, PR and CR should be confirmed by a repeat tumor imaging assessment no less than 4 weeks from the date the response was first documented. Therefore, the scan for confirmation of response may be performed at the earliest 4 weeks after the first indication of response, or at the next scheduled scan (9 or 12 weeks later), whichever is clinically indicated. Subjects will then return to regular scheduled imaging Q9W (or Q12W), starting with the next scheduled imaging time point. Subjects who obtain a confirmation scan do not need to undergo the next scheduled tumor imaging if it is <4 weeks later; tumor imaging may resume at the subsequent scheduled imaging time point.

Per irRECIST (section 7.1.2.6.7), disease progression should be confirmed by the site at least 4 weeks after site-assessed first radiologic evidence of PD in clinically stable subjects. Subjects who have unconfirmed disease progression may continue on treatment at the discretion of the site investigator until progression is confirmed by the site provided they have met the conditions detailed in Section 7.1.2.6.7. Subjects who obtain a confirmation scan do not need to undergo the next scheduled tumor imaging if it is <4 weeks later; tumor imaging may resume at the subsequent scheduled imaging time point if clinically stable. Subjects who have confirmed disease progression as assessed by the site will discontinue the treatment. Exception is detailed in Section 7.1.2.6.7.

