2.1.2 Trial Diagram at Individual Subject Level

This section applies to all subjects who have enrolled to the study. The study includes a 28-day Screening Period, a Study Treatment Period and a Disease/Survival Follow-up Period. Subjects must have measurable disease per RECIST 1.1, as confirmed by the BICR, and must have provided adequate tumor tissue samples in order to be eligible. After an eligible subject is enrolled, the subject will receive pembrolizumab monotherapy 200 mg Q3W via intravenous (IV) infusion until confirmed disease progression as assessed by the investigator, unacceptable toxicity, death, withdrawal of consent, or having received 35 administrations (approximately 2 years) of pembrolizumab treatment without disease progression. In order to prevent premature study treatment discontinuation due to pseudoprogression, immune-related RECIST (irRECIST) will be used for confirmation of disease progression (refer to Section 7.1.2.6.7 for details). Decisions regarding stopping pembrolizumab after a confirmed complete response (CR) and guidelines on retreatment are detailed in Section 7.1.5.2.1.

During study treatment period, subject will have clinic visits Q3W for safety assessments and pembrolizumab infusion. Imaging-based disease assessments will occur every 9 weeks (Q9W) from study entry until Week 54 and every 12 weeks (Q12W) thereafter until disease progression is determined by the investigator per irRECIST, subject's death, withdrawal of consent, initiation of a new anti-cancer therapy, study completion or early termination. Cancer antigen 125 (CA125) will be collected at baseline and at the time of each imaging assessment, However, CA125 should not be used by the investigator to determine disease progression in this study. The trial diagram at subject level is depicted in [Figure 2](#) in Section 2.2.

Specific procedures to be performed during the trial, as well as their prescribed times and associated visit windows, are outlined in the Trial Flow Chart - Section 6.0. Details of each procedure are provided in Section 7.0 – Trial Procedures.

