7.1.2.6.4 End of Treatment and Follow-up Tumor Imaging

In subjects who discontinue trial treatment without documented disease progression, every effort should be made to continue monitoring their disease status by tumor imaging using the same imaging schedule used while on treatment (Q9W (63 days \pm 7 days) from the date of allocation up to 54 weeks with subsequent imaging performed Q12W (84 days \pm 7 days).) to monitor disease status until (1) the start of new anti-cancer treatment, (2) disease progression, (3) death, or (4) the end of the study, whichever occurs first.

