Any subject deemed clinically unstable should be discontinued from trial treatment at site-assessed first radiologic evidence of PD and is not required to have repeat imaging for PD confirmation.

In determining whether or not the tumor burden has increased or decreased per irRECIST, the investigator should consider all target and non-target lesions as well as any incremental new lesion(s).

Scenarios where PD is not confirmed at repeat imaging if ALL of the following occur by irRECIST:

- Target lesion sum of diameters is <20% or <5 mm absolute increase compared to nadir
- Non-target disease resulting in initial PD is qualitatively stable or improved
- New lesion resulting in initial PD is qualitatively stable or improved
- No incremental new lesion(s) since last evaluation
- No incremental new non-target lesion progression since last evaluation

If repeat imaging does not confirm PD per irRECIST as assessed by the investigator and the subject continues to be clinically stable, study treatment tumor imaging assessment may continue per study schedule.

Scenarios where PD is confirmed at repeat imaging if ANY of the following occurs by irRECIST:

- Target lesion sum of diameters remain $\geq 20\%$ and at least 5 mm absolute increase compared to nadir
- Non-target disease resulting in initial PD is qualitatively worse
- New lesion resulting in initial PD is qualitatively worse
- Additional new lesion(s) since last evaluation
- Additional new non-target progression since last evaluation

If repeat imaging confirms PD due to any of the scenarios listed above, subjects will be discontinued from study therapy.

NOTE: If a subject has confirmed radiographic progression (i.e., 2 scans at least 4 weeks apart demonstrating progressive disease) per irRECIST, but the subject is achieving a clinically meaningful benefit and there is no further increase in the tumor burden at the confirmatory tumor imaging, an exception to continue treatment may be considered following consultation with the Sponsor. In this case, if treatment is continued, tumor imaging should continue to be performed following the intervals as outlined in Section 6.0 (Trial Flowchart) and be submitted to the central imaging vendor.

Additional details about irRECIST are referenced in Merck TIP Sheet for RECIST 1.1 and irRECIST.

Table 5 irRECIST Imaging and Treatment after First Radiologic Evidence of PD

	Clinically Stable		Clinically Unstable	
	Imaging	Treatment	Imaging	Treatment

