First radiologic evidence of PD by RECIST 1.1	Repeat imaging at ≥ 4 weeks at site to confirm PD	May continue study treatment at the Investigator's discretion while awaiting confirmatory scan by site	Repeat imaging at ≥ 4 weeks to confirm PD per physician discretion only	Discontinue treatment
Repeat scan confirms PD by irRECIST at the local site	No additional imaging required	Discontinue treatment (exception is possible upon consultation with Sponsor).	No additional imaging required	N/A
Repeat scan shows SD, PR or CR by irRECIST at the local site*	Continue regularly scheduled imaging assessments	Continue study treatment at the local site Investigator's discretion	Continue regularly scheduled imaging assessments	May restart study treatment if condition has improved and/or clinically stable per Investigator's discretion. Next tumor imaging should occur according to the regular imaging schedule outlined in the protocol.
* SD,PR and CR for irRECIST are identical to RECIST 1.1				

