3.6 Statistical Methods

3.6.1 Statistical Methods for Efficacy Analyses

This section describes the statistical methods that address the primary and secondary objectives.

Data from the training set (first 100 subjects in Cohort A) will be evaluated for biomarker analysis and cut point determination. Subjects who did not meet Treatment-free Interval/Platinum-free Interval inclusion criteria for Cohort A would be excluded from the cut point determination analysis.

Efficacy will be evaluated in the *All Comer* group and the PD-L1_H subgroup for Cohort A and B respectively. For the primary efficacy endpoint, the ORR based on RECIST 1.1 by the BICR, the point estimate, and 95% confidence interval (as determined by the upper and lower 97.5% one-sided confidence bounds) will be provided using an exact binomial distribution. Secondary efficacy evaluations of ORR based on RECIST 1.1 by investigator review, DCR based on RECIST 1.1 by the BICR and ORR based on irRECIST by BICR will also be conducted using the same methodology as for the primary efficacy analysis. Subjects without response data will be counted as non-responders and disease not controlled.

Duration of response by BICR and investigator review will be summarized using Kaplan-Meier method in all responders.

For PFS and OS, Kaplan-Meier (KM) curves, median estimates, and survival at 6, 12 and 18 months based on the KM curves (95% CI is based on Greenwood's formula) will be provided as appropriate. Subjects without efficacy evaluation data or without survival data will be censored at Day 1. The restricted Mean Survival Time estimate of PFS and OS will also be calculated and plotted over time. Censoring rules for DOR and PFS are summarized in [Table 1](#) and [Table 2](#) respectively.

Table 1 Censoring Rules for Analyses of DOR

Situation	Date of progression or censoring	Outcome
No progression nor death, no new anti-cancer therapy initiated	Last adequate assessment	Censor (non-event)
No progression nor death, new anti-cancer therapy initiated	Last adequate assessment before new anti-cancer therapy initiated	Censor (non-event)
Death or progression after ≥ 2 consecutive missed adequate disease assessments	Last adequate assessment prior to ≥ 2 missed adequate disease assessments	Censor (non-event)
Death or progression after ≤ 1 missed adequate disease assessments	Death or progression	End of response (Event)

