A missed disease assessment includes any assessment that is not obtained or is considered inadequate for evaluation of response.		

Table 2 Censoring Rules for Analyses of PFS

Situation	Date of progression or censoring
No PD and no death; new anticancer treatment is not initiated	Censored at last disease assessment
No PD and no death; new anticancer treatment is initiated	Censored at last disease assessment before new anticancer treatment
PD or death documented after ≤ 1 missed disease assessment	Progressed at date of documented PD or death
PD or death documented after ≥ 2 missed disease assessments	Progressed at date of documented PD or death

An outline of the key efficacy analysis strategy is presented in [Table 3](#).

Table 3 Analysis Strategy for Key Efficacy Endpoints

Endpoint	Statistical Method	Analysis Population	Missing Data Approach

 • ORR by BICR per RECIST1.1 • ORR by investigator assessment per RECIST1.1 	Exact test of binomial parameter; 95% CI [†]	ASaT	Subjects with missing data are considered non-responders

 • DOR by BICR per RECIST1.1 • DOR by investigator assessment per RECIST1.1 	Summary statistics using Kaplan-Meier method	All responders	Refer to Table 1

 • PFS by BICR and investigator assessment per RECIST 1.1 	Summary statistics using Kaplan-Meier method	ASaT	Refer to Table 2

 • DCR by BICR and investigator assessment per RECIST 1.1 	Exact test of binomial parameter; 95% CI [†]	ASaT	Subjects with missing data are considered disease not controlled

 • OS 	Summary statistics using Kaplan-Meier method	ASaT	Censored at last known alive date
[†] 95% confidence interval is determined by the upper and lower 97.5% one-sided confidence bounds.			

The strategy to address multiplicity issues with regard to multiple endpoints and interim analyses is described in Section 3.7, Interim Analyses and in Section 3.8, Multiplicity.

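### Imaging stops on the site's call of progression with no central check, so BICR PFS and DOR may be overstated by an amount the documents do not fix

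*Combined protocol and SAP*

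**What the plan says.** **When imaging ends.** Protocol Section 7.1.2.6.2 gives the stopping rule without naming who judges it: "Imaging assessments should continue until disease progression per RECIST 1.1 or to confirm disease progression per irRECIST". Other places name the site:

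- Section 2.1.2 runs scheduled imaging "until disease progression is determined by the investigator per irRECIST".
- Section 7.1.2.6.2 adds that "disease progression should be confirmed by the site at least 4 weeks after site-assessed first radiologic evidence of PD in clinically stable subjects".
- Section 7.1.2.6.7, Table 5, says of a subject whose repeat scan confirms progression locally: "No additional imaging required".
- The same section says a clinically unstable subject "is not required to have repeat imaging for PD confirmation".
- The flow chart (Section 6.1, note b) moves subjects to telephone contact after local progression or new therapy.
- Section 7.1.2.6.4 has subjects who stop treatment without progression imaged "until (1) the start of new anti-cancer treatment, (2) disease progression", death or study end.

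**What the central reader does.** Section 7.1.2.6 sends the images to the central vendor, and Section 7.1.2.6.1 has the vendor confirm measurable disease before allocation. No section has it verify progression before scanning stops.

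**What is analysed.** PFS and DOR by BICR are secondary in every group, with PFS rates at 6, 12 and 18 months (protocol Section 3.2; sSAP 3.4.1). Investigator-assessed versions are planned too. After new therapy without progression or death, sSAP Table 1 (DOR) censors at "Last adequate assessment before new anti-cancer therapy initiated", and sSAP Table 2 (PFS) reads "Censored at last disease assessment before new anticancer treatment". No discordance count or related sensitivity analysis is planned.

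**The concern.** The person who ends imaging is not the person whose reads define the endpoint. Once the site calls progression and scanning stops, BICR may never see the later scan on which it would have agreed. Such a subject is likely to be nearer progression than others still under observation, so treating her as progression-free at that point, or until death, makes the curve too high.

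Protocol Section 4.2.3.1 relies on durability of response and PFS rates to describe activity. The trial has one arm, so no control group shares the bias, and every result is an estimate, so an estimate's accuracy is all there is to protect. The primary ORR is not the subject of this point.

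**Working it through.** The documents state no expected PFS or DOR and no BICR/site discordance rate, so there is no planned figure to reproduce. The check is of the censoring rules, then an illustration of size.

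**1. What the sSAP does with a subject whose progression only the site has called**

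| Later course | BICR DOR (Table 1) | BICR PFS (Table 2) |
|---|---|---|
| Alive at cut-off | Censored | Censored |
| Dies after at most 1 missed assessment | Event at death | Event at death |
| Dies after 2 or more missed assessments | Censored before the gap | Event at death |

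Table 2's new-therapy row applies only where there is no death. DOR therefore has informative censoring. PFS has mostly late-dated events, with censoring confined to those alive at cut-off.

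**2. How many are censored**

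Assumption: exponential survival after site progression, median 7.5 months, so h(t) = 2^(−t/7.5).

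- DOR: two 9-week intervals are 18 × 7/30.4375 = 4.14 months. Deaths by then: 1 − h(4.14) = 1 − 0.682 = 0.318. About 68% are censored.
- PFS: by simulation, about 5% are censored at the final cut-off (36–48 months after entry) and about 46% at a cut-off 8–20 months after entry.

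**3. Size for 6-month PFS with a one-scan lag**

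Inputs:
- Scans at Weeks 9, 18 and 27, that is 2.07, 4.14 and 6.21 months (protocol).
- Median m = 3 to 5 months (the range protocol Section 4.1.1.1 gives for single agents), with S(t) = 2^(−t/m) for BICR progression.
- A share q = 10–30% called by the site one scan earlier (assumption).

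The excess just after the Week 27 scan comes from subjects whose BICR progression at Week 18 or 27 goes unseen and who are still alive:

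Δ = q × {[S(2.07) − S(4.14)] × h(4.14) + [S(4.14) − S(6.21)] × h(2.07)}, with h(4.14) = 0.682 and h(2.07) = 0.826.

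- m = 3: S = 0.620, 0.384, 0.238. The bracket is 0.236 × 0.682 + 0.146 × 0.826 = 0.161 + 0.121 = 0.282. Δ = 2.8 points (q = 10%) to 8.5 (q = 30%).
- m = 5: S = 0.751, 0.563, 0.423. The bracket is 0.188 × 0.682 + 0.140 × 0.826 = 0.128 + 0.116 = 0.244. Δ = 2.4 to 7.3 points.

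Simulation on the same assumptions gave about +2 to +9. If half of the discordant subjects have a confirmatory scan that BICR reads as progression, Δ halves: 1.2 to 4.2, or about +1 to +4.

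**4. Longer lags and later times**

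With a two-scan lag, the first BICR progression lost is at Week 27, or 6.21 months. At exactly 6.0 months the excess is therefore nil. Just after that scan, with m = 3, it is q × 0.146 × 0.682 = 1.0 to 3.0 points.

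A second simulation (60,000 subjects) put the exponential on the site's date instead, with median 3.4 or 5.0 months for PFS and 6 or 10 months for DOR. Planned analysis minus imaging to BICR progression, in points:

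| Endpoint | Lag 1 scan | Lag 2 scans | Lag 4 scans |
|---|---|---|---|
| PFS, 6 months | +2 to +7 | 0 | 0 |
| PFS, 12 months | +3 to +12 | +3 to +10 | +1 to +4 |
| DOR, 6 months | +1 to +3.5 | 0 to −1 | 0 to −1 |
| DOR, 12 months | +2 to +8 | +1.5 to +5 | 0 to +1 |

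The simulations have no dropout and no death before site progression. Figures near 6 months depend on which side of the Week 27 scan the curve is read, so the top of the range is a scenario and not a ceiling.

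**The case against.** The strongest reply has four parts.

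- **Confirmatory scan.** Clinically stable subjects are rescanned at least 4 weeks after the site's first call, and that scan goes to the central vendor. BICR PFS by RECIST 1.1 needs no confirmation of progression, so BICR often sees the scan that matters. This stands and reduces the effect. It does not help clinically unstable subjects, who need no repeat scan, or those who start new therapy first. A reader might infer that nobody is scanned after the site's first call; the protocol does not say that.
- **PFS deaths.** A reader might infer that sSAP Table 2 censors every site-only progressor. It does not: a later death is an event even after two or more missed assessments. This changes the mechanism for PFS, but an event dated at death is still later than the BICR progression it replaces.
- **Investigator PFS and DOR are already planned.** They date progression at the site's call and allow a comparison. They do not keep the BICR responder set, count new therapy as an event, or show how many BICR results rest on imaging that the site ended.
- **The endpoints are secondary and untested.** True, and it limits the weight of the point. With no hypothesis tests anywhere in the trial, it is not a reason to leave the estimates unqualified.

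**Conclusion.** The concern holds as a possible upward bias of unknown size. Imaging follows the site, BICR does not verify progression before scanning stops, and the sSAP has no analysis that would show the consequence. For DOR the route is informative censoring. For PFS it is mainly late-dated deaths, with censoring of those alive at cut-off. Exposure is greatest in clinically unstable subjects.

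The illustrative size is about +1 to +9 points on 6-month PFS. It rests on assumed 10–30% discordance, a one-scan lag, a 3–5 month median and a 7.5-month median survival after site progression; the low end also assumes that half of the discordant subjects have a confirmatory scan BICR calls progression. If BICR progression would have come two or more scans later, the 6-month effect is near zero, though some remains at 12 months.

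A reader might go further and say that BICR PFS and DOR are overstated. The documents do not support that, because they give neither a discordance rate nor the delay between the two reads.

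**What to change.** Add to sSAP 3.6.1:

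1. A sensitivity analysis of BICR PFS, and of DOR among BICR responders, in which the event is the earliest of BICR progression, site-assessed RECIST 1.1 progression, new anti-cancer therapy or death.
2. A table of the number of subjects with site progression but no BICR progression, by cohort and group.
3. Both shown beside the BICR estimates and the investigator estimates already planned.

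It would also help to state explicitly in Table 2 that a death after new therapy counts as an event, if that is the intention.

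The cost is programming on data already collected; no scan, visit or sample-size change is needed. The added estimate will look less favourable. It should be labelled a conservative lower bound, because it counts mistaken site calls, and therapy switches made for other reasons, as events.
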